- Spatial and temporal distribution of dengue cases (confirmed and probable symptomatic cases and inapparent infections).

- *Spatial and temporal distribution of laboratory confirmed and probable Zika virus cases*
- *Spatial and temporal distribution of patients with laboratory confirmed and probable chikungunya virus infection*
- *Occurrence of laboratory confirmed or probable Zika and/or chikungunya infection in suspected dengue cases (differential diagnosis of dengue), retrospectively*
- *Antibody titre against Zika and chikungunya virus at the scheduled visits*

Section 8.5.4 Analysis of tertiary objectives

Analysis of tertiary objectives is optional and may or may not be performed. If these analyses are performed, they will be conducted by the Research and Development Department. Statistical methods for tertiary objectives will be described in the SAP.

The neutralization assay, if performed, will only be done on blood samples from a subset of subjects. YF virus antibody testing will be performed retrospectively, for subjects in YF endemic region and who was tested positive for dengue.

Analysis of risk factors for symptomatic dengue

Poisson regression models will be used for exploring the risk factors (e.g. region, age and gender, etc.) for symptomatic dengue. The analyses will account for clustering of observations within households for the analyses by centre and also the stratification by centres for the overall analyses.

Incidence rates of symptomatic Zika infections

The following analyses will be performed by study site, gender and age-group, previous dengue exposure and previous Zika infection:

- *Incidence rate of laboratory-confirmed or probable symptomatic Zika infection with 95% CI for each season separately: the numerator will be the number of subjects with lab-confirmed or probable symptomatic Zika infection during the season (between the visits scheduled before and after the season). The denominator will be the total person-years at risk, i.e. from the visit scheduled before the season until the first lab-confirmed or probable symptomatic Zika infection during the season, the next scheduled visit or the subject's withdrawal, whichever comes first.*
- *Incidence rate of laboratory-confirmed or probable symptomatic Zika infection with 95% CI all seasons combined: the numerator will be the number of subjects with lab-confirmed or probable symptomatic Zika infection during the study Zika follow-up period. The denominator will be the total person-years at risk, i.e. from start of the study Zika follow-up period until the first lab-confirmed or probable symptomatic Zika infection, the end of the study or the subject's withdrawal, whichever comes first.*

Incidence rates of symptomatic chikungunya infections

The following analyses will be performed by study site, gender and age-group, previous dengue exposure and previous chikungunya infection:

- *Incidence rate of laboratory-confirmed or probable symptomatic chikungunya infection with 95% CI for each season separately: the numerator will be the number of subjects with lab-confirmed or probable symptomatic chikungunya infection during the season (between the visits scheduled before and after the season). The denominator will be the total person-years at risk, i.e. from the visit scheduled before the season until the first lab-confirmed or probable symptomatic chikungunya infection during the season, the next scheduled visit or the subject's withdrawal, whichever comes first.*
- *Incidence rate of laboratory-confirmed or probable symptomatic chikungunya infection with 95% CI all seasons combined: the numerator will be the number of subjects with lab-confirmed or probable symptomatic chikungunya infection during the study chikungunya follow-up period. The denominator will be the total person-years at risk, i.e. from start of the study chikungunya follow-up period until the first lab-confirmed or probable symptomatic chikungunya infection, the end of the study or the subject's withdrawal, whichever comes first.*

Analysis for Zika and chikungunya viruses in suspected dengue cases

The proportions and associated exact 2-sided 95% confidence intervals (CI) of the Zika and chikungunya viruses in suspected dengue cases will be summarized.

Analysis for seroprevalence of antibody titers against Zika and chikungunya viruses at selected timepoints

Seroprevalence at each selected timepoint will be calculated as a proportion i.e. the number of seropositive samples at each selected timepoint over the total number of samples with antibody results. An exact 95% CI will be computed.

Section 9.3 Archiving of data at study sites

Following closure of the study, the investigator must maintain all site study records in a safe and secure location. The records must be maintained to allow easy and timely retrieval, when needed (e.g. audit or inspection), and, whenever feasible, to allow any subsequent review of data in conjunction with assessment of the facility, supporting systems, and staff. Where permitted by applicable laws/regulations or institutional policy, some or all of these records can be maintained in a validated format other than hard copy (e.g. microfiche, scanned, electronic for studies with an eCRF); however, caution needs to be exercised before such action is taken. The investigator must assure that all reproductions are legible and are a true and accurate copy of the original and meet accessibility and retrieval standards, including re-generating a hard copy, if required. Furthermore, the investigator must ensure there is an acceptable back-up of these reproductions and that an acceptable quality control process exists for making these reproductions.

GSK will inform the investigator/institution of the time period for retaining these records to comply with all applicable regulatory requirements. However, the investigator/institution should seek the written approval of the sponsor before proceeding with the disposal of these records. The minimum retention time will meet the strictest standard applicable to that site for the study, as dictated by ICH GCP or other applicable guidelines any institutional requirements or applicable laws or regulations, or GSK standards/procedures; otherwise, the minimum retention period will default to ~~15~~ 25 years.

The investigator/institution must notify GSK of any changes in the archival arrangements, including, but not limited to, the following: archival at an off-site facility, transfer of ownership of the records in the event the investigator leaves the site.

Section 11 References

Boletim Epidemiológico - Volume 48 - n 05 - 2017 - Secretaria de Vigilância em Saúde – Ministério da Saúde. Accessed at : http://combateaedes.saude.gov.br/images/pdf/2017-Dengue_Zika_Chikungunya-SE4.pdf. Accessed on 22 August 2016.

Appendix B Structured script

Are you aware of dengue, *chikungunya or Zika* cases in your neighborhood during the past month?

Any subject that meets the case definition for suspected dengue, *chikungunya or Zika* the subject (and subject's parent(s)/LAR(s) as applicable) will be referred to the study hospital according to protocol

1. DOCUMENT HISTORY

Date	Description	Protocol Version
29-OCT-2019	Amendment 1*	Amendment 4: 16 Oct 2017
14-JUN-2019	Final version	Amendment 3: 09 JAN 2015

[figure not shown]
- * In 2017 GSK vaccines has decided to terminate the development of a dengue vaccine. Accordingly none of the tertiary objectives will be evaluated and the analyses additional to those planned in the protocol have been removed from the first statistical analysis plan. In addition in light of the low number of dengue episodes, the large number of positive anti-dengue IgG at visit 1 and the number of dengue cases reported outside the season,
- (1) The analyses of PCR confirmed cases (only 10 cases) and the analyses of secondary dengue infections were removed.
 - (2) The analyses by seroprevalence at each visit were removed,
 - (3) The analyses by season were removed. Only the analyses by calendar year are to be conducted
 - (4) Subjects without seroprevalence status at visit 1 were removed from the ATP cohort because serological status of symptomatic/inapparent dengue infections cannot be assessed properly for such subjects
 - (5) Planned analyses of medical and vaccination history were removed.
 - (6) The statistical method was updated to ignore the household cluster effect and to provide incidence rate with confidence interval in absence of dengue episodes in a calendar year for a study site .

2. STUDY DESIGN

2.1. Study design overview

- **Type of design:** Prospective, multicenter, community-based, household-sampling, cohort study in Brazil.
- **Duration of the study:** The study period per initial site, initially planned to be one year, was planned to be extended by additional three years (overall four years) to cover three additional dengue seasons. The study period for any new site was planned to be 3 years.
- **Enrolment wave:** There were 2 waves of enrolment for recruiting the planned 3600 subjects:
 - Initial Cohort = about 1800 subjects planned – four years follow-up planned – INITIAL sites: Rio (PPD), Manaus (PPD) and Salvador (PPD).
 - Expansion Cohort = about 1800 subjects planned – three years follow-up planned – planned NEW sites: Natal (PPD), Campo Grande (PPD), and Campinas (PPD).
- **Replacement:** replacement subjects were enrolled in order to compensate for subjects who did not wish to extend their participation for three additional years (for subjects from the initial cohorts), subjects who prematurely terminated participation or subjects who were lost to follow-up (for subjects from the initial and expansion cohorts).
- This was done to maintain a cohort size of at least 500 subjects per site, in the initial and expansion cohorts, at the beginning of each additional study year/season.

• **Schematic representation of the scheduled visits:**

V=Visit

The scheduled visits for initial cohort subjects are shown in black

New enrolments were to be done yearly (as needed) till the end of study Year 3 of each study site

Enrollment of expansion cohort subjects started preferably during study Year 2

For replacement subjects, the number of visits depended on the year enrolled

- **Type of study:** self-contained.
- **Data collection:** Electronic Case Report Form (eCRF).
- **Study termination:** in December 2017, GSK decided to deprioritise the development of the dengue purified inactivated vaccine (DPIV) candidate and to terminate the study EPI-DENGUE-006 at the study visit planned after the 2018 dengue season. This decision was made due to the scientific challenges and development risks associated with the candidate vaccine. The planned study site in Campo Grande was not initiated before the decision of study termination was taken, so no subjects were enrolled in that site.

2.2. Study population

This study planned to enrol subjects (six months of age and older at the time of enrolment) from randomly selected households from different communities within the selected sites.

2.2.1. Selection of study sites

Five sites covering different regions of the country were selected for this study. Selection criteria of the sites include support from the Family Health Physician Program (FHP), the Larval Index Rapid Assay (LIRA) or with field research experience in the community. Other selection criteria of the sites include an extensive feasibility assessment that includes aspects related to the site structure including laboratory and local facilities, availability of the principal investigator and previous experience on Dengue.

The FHP is a Brazilian government public health strategy that consists of multidisciplinary teams of health care workers that cover geographically defined areas to provide basic/preventive care to community members. The teams include a doctor, a nurse, a nurse auxiliary, and community health care workers who pay regular visits to the

household under its responsibility to deliver health promotion activities and facilitate triage and referral into the health unit, among other activities. Community health care workers are local residents who are trained for basic tasks.

LIRA is an alternative vector surveillance strategy that consists of random sampling of a number of dwellings in which surveillance of *Aedes*-positive breeding places is carried out to identify where there is a risk of mosquito reproduction, and has been widely implemented in Brazil [[Pontes](#), 2000].

The study sites in Rio, Salvador, Natal and Campinas were selected mainly considering their experience in previous Dengue field research. Manaus was selected mainly for the experience of its principal investigator in dengue studies and the previous experience of the site in clinical trials with GSK.

At least one community of households within each site was selected.

2.2.2. Selection of communities

- Community selection was based on the following characteristics: 1) preferably areas where the Brazilian FHP or LIRA has been fully implemented or where access to the community is already established by a government program, e.g., registry of families by Secretary of Health, or other institutional program, such as university, in order to allow for random sampling of households; 2) safe access by study personnel; 3) high population density; and 4) low migration rate.

2.2.3. Selection of households

Households were to be randomly selected through LIRA strategy or from a list provided by the FHP or equivalent.

The FHP or LIRA provided an exhaustive list of households to the study sites and served as the liaison between the study personnel and the household, and had not any other role in this study.

Sites with access to LIRA (i.e. Manaus, Natal and Campinas) use LIRA's specific sampling strategy. LIRA's sampling strategy (preferred strategy) consists of dividing the administrative neighbourhoods of the city into blocks in which each building is enumerated by a unique code number. Within each block a corner is chosen and moving leftward, one in every four houses is systematically selected for vector inspection.

Where LIRA was not implemented but has FHP coverage, a random sample of households was to be selected from the FHP database. Note that none of the five study sites part of the final analysis had FHP coverage.

Where another type of household registry offers the only access to the community (i.e. Rio and Salvador), a random sample was to be drawn from the registry database.

Actually, for Rio, Salvador, Natal and Campinas, contact in the communities was performed to identify potential subjects who were interested to be enrolled. In addition, households were selected based on their location (in more safety areas and near to the Unit of Health Care).

2.2.4. Selection of subjects

At least 3600 subjects were planned to be recruited in the study in 2 waves of enrolment. Each wave, initial and expansion cohorts, enrolled about 600 subjects per site in order to maintain at least 500 subjects per site at the beginning of each dengue season.

Preferably the recruitment period was planned to occur outside of the peak dengue transmission season, and continued until each site has reached its foreseen target. Recruitment of replacement subjects were done during the low dengue transmission.

If the target household was found empty or all members refused to participate, the first household to the left was approached. Those households refusing to participate were recorded as such. A household refusal was characterized when all individuals in the household refused to participate in the study. Individual refusals in a given household were not preclude inclusion of other individuals living in the households, and were recorded as such. Information on refusal was kept at the study site and was not recorded in the screening/enrolment log.

In the subsequent study years/seasons, the cohort size was maintained at a minimum of 500 subjects per site. Since subjects who prematurely terminate participation and/or lost to follow-up were replaced, the final number of participants across the four planned study years may exceed 3600 subjects. Yearly, there was an evaluation of active subjects. If the number of active subjects/site became < 500 , there were enrolment of replacement subjects to maintain a cohort size of at least 500 subjects per site. Recruitment of replacement subjects could have occurred at the end of the planned study year 1, 2 or 3. The recruitment approach was the same as for the initial enrolment. Replacement subjects were enrolled from households located in the same communities as the withdrawn subjects.

In order to better represent the Brazilian population distribution, subjects enrolled in the expansion cohorts should be composed of at least 30% of subjects younger than 18 years old and should not exceed 20 % of adults 50 years or older. Subjects enrolled as replacement subjects for the initial and expansion cohorts were recruited to approach as much as possible a minimal representation of 30% of subjects younger than 18 years old and a maximal representation of 20% for adults 50 years or older. This strategy was implemented at enrolment in Salvador, Natal and Campinas and for replacement subject in Rio.

2.3. Dengue case detection

All study subjects with suspected dengue should have been seen at a designated study hospital or clinic by the study physician.

For the five study sites, the designated study hospitals/clinics are not the investigator sites. The designated study hospitals/clinics are working with the investigator sites and are located in the community where the subjects live.

Suspected cases in the study may arise from three sources:

1. Referred by study personnel during scheduled home visits
2. Through enhanced passive surveillance
3. As a result of active surveillance between scheduled visits

2.3.1. Case detection during scheduled home visits

If a subject was identified as suspected case during any home visit, he or she was referred to the designated study hospital/clinic for medical evaluation.

Note that the home visits are denoted as scheduled study visits in the list of study procedures in the protocol.

2.3.2. Case detection through enhanced passive surveillance

The subject/subject's parent(s)/legally acceptable representative (LAR[s]) was instructed to contact the study staff (the local study coordinator) at any time dengue was suspected (i.e., body temperature $\geq 38^{\circ}\text{C}$ measured (by any route) for at least two consecutive days).

The subject/subject's parent(s)/LAR(s) was instructed to contact the hospital or study clinic should the subject manifest any signs or symptoms they/the subject's parent(s)/LAR(s) perceive as an emergency or severe.

The local study coordinator then arranged for an appointment at the designated study hospital/clinic.

Although subjects were instructed to contact the study staff in the event of suspected dengue, there may have been cases where the subject was taken directly to the hospital or clinic. If this occurred when the study physician was not available, the staff at the designated hospital should have notified the local study coordinator and the study physician.

2.3.3. Case detection through active surveillance

Telephone calls (or home visits when applicable, if a phone call was not feasible) were conducted at least monthly and more frequently if needed. During the phone call or visit, a structured script was used to inquire about dengue symptoms since the last contact.

If dengue was suspected during active surveillance, an appointment was arranged at the designated study hospital/clinic, and at least one additional visit was required for case follow-up.

2.4. Dengue seasons

Dengue season:

Region/study site name (site number)	Dengue season
Rio (PPD)	1st January to 30th June
Manaus (PPD)	1st January to 30th June
Salvador (PPD)	1st January to 30th June
Natal (PPD)	1st January to 30th June
Campinas (PPD)	1st January to 30th June

3. OBJECTIVES**3.1. Primary objective**

- To estimate the incidence of laboratory-confirmed symptomatic dengue infection in the study population by year/season.

3.2. Secondary objectives

- To estimate the serotype-specific incidence of virologically-confirmed symptomatic dengue infection in the study population overall and by season.
- To estimate the incidence of symptomatic dengue infection (including laboratory-confirmed and probable cases) in the study population by study site, gender, age-group, previous dengue exposure (primary or secondary), overall and by season.
- To estimate the prevalence of previous dengue infection (dengue seroprevalence) in the study population overall and by study site, gender and age-group at enrolment.
- To estimate the incidence of primary inapparent dengue infection, in the study population overall and by study site, gender age-group and by season.
- To describe symptoms and spectrum of dengue disease in the study population.

3.3. Tertiary objectives (optional)

- To investigate potential risk factors for symptomatic dengue infection.
- To investigate the role of dengue neutralizing antibodies elicited through natural infection in protection against subsequent infection.
- To estimate the degree of underreporting of dengue cases using the passive national notification surveillance.
- To describe previous Yellow Fever (YF) antibody profile in selected dengue cases to investigate the role of previous YF immunity on the dengue neutralizing antibody profile following dengue infection.
- To describe the spatial and temporal distribution of dengue cases among cohort participants in the study areas.

4. ENDPOINTS

4.1. Primary endpoint

- Laboratory-confirmed symptomatic dengue infection (all DENV types).

4.2. Secondary endpoints

- DENV-type specific primary laboratory-confirmed symptomatic dengue infection.
- DENV-type specific secondary laboratory-confirmed symptomatic dengue infection.
- Primary symptomatic dengue infection (including laboratory-confirmed and probable cases).
- Secondary symptomatic dengue infection (including laboratory-confirmed and probable cases).
- Previous dengue infection(s) (dengue seroprevalence) at baseline.
- Primary inapparent dengue infection.
- Severity of symptoms of symptomatic dengue (using the 2009 WHO guidelines).

4.3. Tertiary endpoints

Exploratory objectives may be assessed based on, but not limited to the following endpoints:

- Risk factors for dengue infection and disease.
- Neutralizing antibodies titers against DENV 1-4.
- Neutralizing antibody titers against YF virus.
- Spatial and temporal distribution of dengue cases (confirmed and probable symptomatic cases and inapparent infections).

5. ANALYSIS SETS

5.1. Definition

The following analysis sets are defined:

Analysis Set	Description
Total cohort	All subjects enrolled in the study
Total cohort without subjects with code 900	All subjects from the Total cohort without elimination code 900
ATP cohort	All subjects from the Total cohort without subjects with code 900, who met all inclusion/exclusion criteria (code 2010) and had seroprevalence status at visit 1 (code 2020)

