8.5. Statistical methods

Any deviation or change from the original statistical plan will be described and justified in the final study report.

All the analyses of primary objectives will be performed on the ATP cohort. Analysis of demographics will be performed on the total cohort.

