5.2.2. Elimination from ATP cohort

Code 900 (invalid informed consent or fraudulent data) and code 2010 (Protocol violation linked to the inclusion/exclusion criteria) will be used for identifying subjects eliminated from ATP cohort.

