6.2. Laboratory-confirmed symptomatic dengue case

Early presenter:

At least one of the following findings must be met for a laboratory-confirmed dengue case:

- Dengue virus identification through RT-qPCR on the acute serum sample
- Dengue virus NS1 positive on acute serum sample through ELISA.
- Anti-dengue IgM seroconversion between acute and convalescent serum samples through ELISA.

Late presenter:

- Anti-dengue IgM seroconversion between acute and convalescent serum samples through ELISA.

Acute and convalescent serum samples are samples taken at the first and follow-up visits for suspected dengue case, respectively.

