7.2.2. Additional considerations

7.2.2.1. Incidence rate

In light of the low number of dengue episodes, the large number of positive anti-dengue IgG at visit 1 and the number of dengue cases reported outside the season,

1. The analyses of PCR confirmed cases (only 10 cases) and the analyses of secondary dengue infections were removed.
2. The analyses by seroprevalence at each visit were removed,
3. The analyses by season were removed. Only the analyses by calendar year are to be conducted

- 4. Subjects without seroprevalence status at visit 1 were removed from the ATP cohort because serological status of symptomatic/inapparent dengue infections cannot be assessed properly for such subjects
- 5. Planned analyses of medical and vaccination history were removed.
- 6. The statistical method was updated to ignore the household cluster effect and to provide incidence rate with confidence interval in absence of dengue episodes in a calendar year for a study site .

Regarding the last point, the expected annual incidence rate for a cohort of subjects followed over a full calendar will be computed using a log-linear model with the number of dengue events (all cases) as depend variable and the total number of subject-month as offset. The model will include the study site, year and month as independent categorical fixed effects (see below).

The expected annual incidence rate in a study site for each year will be estimated as the average of incidence rate over months

```

proc genmod ;
  class center month year;
  model evt= center year month /
    dist=poisson link=log offset=ln TYPE3;

  ods output Estimates=estimc;
  estimate 'center PPD 2014' intercept 12 center 12 0 0 0 0
    year 12 0 0 0 0
    Month 1 1 1 1 1 1 1 1 1 1 1;
  estimate 'center PPD 2014' intercept 12 center 0 12 0 0 0
    year 12 0 0 0 0
    Month 1 1 1 1 1 1 1 1 1 1 1;
  estimate 'center PPD 2014' intercept 12 center 0 0 12 0 0
    year 12 0 0 0 0
    Month 1 1 1 1 1 1 1 1 1 1 1;
  estimate 'center PPD 2014' intercept 12 center 0 0 0 12 0
    year 12 0 0 0 0
    Month 1 1 1 1 1 1 1 1 1 1 1;
  estimate 'center PPD 2014' intercept 12 center 0 0 0 0 12
    year 12 0 0 0 0
    Month 1 1 1 1 1 1 1 1 1 1 1;
  estimate 'overall 2014' intercept 12 center 2.4 2.4 2.4 2.4 2.4
    y 12 0 0 0 0
    Month 1 1 1 1 1 1 1 1 1 1 1;
  estimate 'center PPD 2015' intercept 12 center 12 0 0 0 0
    year 0 12 0 0 0
    Month 1 1 1 1 1 1 1 1 1 1 1;
  estimate 'center PPD 2015' intercept 12 center 0 12 0 0 0

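### SAP Amendment 1 removes subjects without Visit 1 serology from the cohort for the primary incidence rate, which does not use serostatus, and Section 5.2.2 does not list the exclusion

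*SAP*

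**What the plan says.** In SAP Amendment 1 (29 October 2019), Section 5.1 adds to the ATP definition that a subject "had seroprevalence status at visit 1 (code 2020"). Section 7.2.2.1 gives the reason: "Subjects without seroprevalence status at visit 1 were removed from the ATP cohort because serological status of symptomatic/inapparent dengue infections cannot be assessed properly". The document history in Section 1 repeats this.

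Section 5.2.2, which states the elimination codes for the same cohort, says: "Code 900 (invalid informed consent or fraudulent data) and code 2010 (Protocol violation linked to the inclusion/exclusion criteria) will be used". Code 2020 is not mentioned there.

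Section 7.2 of the SAP does not itself name the analysis set for incidence. The link comes from Protocol Section 8.5, "All the analyses of primary objectives will be performed on the ATP cohort", and from the removal being listed under the SAP's incidence-rate heading. The primary endpoint (SAP Section 4.1) is "Laboratory-confirmed symptomatic dengue infection (all DENV types"), with no primary/secondary split.

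**The concern.** A subject with no Visit 1 IgG result can still be under full surveillance, can still have a laboratory-confirmed episode, and still contributes person-time. Dropping that follow-up from the primary rate needs a reason tied to the primary rate, and the SAP's reason concerns the serological status of infections. Most of the analyses that depend on that status, namely secondary infections and results by seroprevalence at each visit, were deleted in the same amendment.

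The amendment itself cites few dengue episodes as its background, so information should not be given up without need. If missing Visit 1 blood is related to age or to willingness to be bled, the rate would also describe a selected group. Separately, a programmer who works from Section 5.2.2 alone would build a different cohort from one who works from Section 5.1.

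**Working it through.** **Does the primary rate need Visit 1 IgG?** Tracing each input:

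- *Case confirmation (SAP 6.2).* Early presenters: RT-qPCR or NS1 on the acute sample, or "Anti-dengue IgM seroconversion between acute and convalescent serum samples through ELISA". Late presenters: the IgM criterion only. Visit 1 IgG is not used.
- *Probable case (SAP 6.4).* IgG on the samples of the illness episode. Visit 1 IgG is not used.
- *Person-time (SAP 11.3.3).* Days of follow-up. Visit 1 IgG is not used.
- *Model (SAP 7.2.2.1).* Site, year and month, with gender and age at Visit 1 as subgroups. Visit 1 IgG is not used.
- *Primary/secondary status, inapparent infection, previous infection (SAP 6.7 to 6.10).* Serology at scheduled visits is needed here.

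One uncertainty remains. The model's dependent variable is described as covering all cases, and the SAP does not define that term. If inapparent infections are counted in it, those events do need serology.

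**What did the previous SAP do?** The 14 June 2019 SAP, Section 5.1, required only no code 900 and all entry criteria met. Its Section 7.4 applied serology in the denominators that need it: inapparent infection and Visit 1 seroprevalence.

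**Which codes apply?** Sections 1, 5.1 and 7.2.2.1 of Amendment 1 all say that the subjects are removed. Section 5.2.2 omits code 2020, and its wording is identical to Section 5.2.2 of the June 2019 SAP. The likely explanation is text that was not updated.

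**Planned precision, reproduced (Protocol 8.2).** Inputs: 3600 enrolled, 9 per 1000 person-years, design effect 1 + (3 − 1) × 0.4 = 1.8, and annual drop-out of 15% (the lower end of the stated 15% to 20%, and the value that reproduces Table 15).

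- Person-years = 3600 × 0.15 / (−ln 0.85) = 3600 × 0.92297 = 3322.7.
- Half-width = 1.96 × √(1.8 × 0.009 / 3322.7) = 0.00433, or 4.33 per 1000.
- Interval 4.67 to 13.33; the protocol states 4.7 to 13.3.
- With the four-year 8611.3 person-years of Table 15: 6.31 to 11.69; the protocol states 6.3 to 11.7.

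**Precision with a share m of person-time removed.** The documents do not give m, so 2%, 5% and 10% are assumed. The half-width is multiplied by 1/√(1 − m). Expected cases over four years are 0.009 × 8611.3 = 77.5, of which 77.5 × m fall in the removed person-time at equal incidence.

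| m | Width factor | One-year interval | Four-year interval | Expected cases removed, four years |
|---|---|---|---|---|
| 2% | 1.010 | 4.63 to 13.37 | 6.28 to 11.72 | 1.6 |
| 5% | 1.026 | 4.56 to 13.44 | 6.24 to 11.76 | 3.9 |
| 10% | 1.054 | 4.44 to 13.56 | 6.17 to 11.83 | 7.8 |

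The width factor does not depend on the design effect, so it also holds under Amendment 1, which ignores household clustering. The case counts are planning figures, not observed ones.

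**Bias.** Let k be the incidence in the removed subjects divided by that in the others (assumed). The ATP rate divided by the full-cohort rate is 1 / [(1 − m) + m·k].

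| m | k = 0.5 | k = 1 | k = 2 | k = 3 |
|---|---|---|---|---|
| 2% | +1.0% | 0 | −2.0% | −3.8% |
| 5% | +2.6% | 0 | −4.8% | −9.1% |
| 10% | +5.3% | 0 | −9.1% | −16.7% |

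**The case against.** The case for the sponsor has substance:

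- Protocol Section 8.3.2 limits ATP to subjects who comply with the protocol's procedures and leaves reasons for elimination to be settled and documented at data cleaning. A Visit 1 blood sample is required of every enrolled subject, so a missed one could fall under that rule.
- The change is disclosed with a reason, and all analyses are descriptive.
- Outputs that depend on serostatus remain: Section 7.3.2 summarises primary diagnosis and inapparent infection on the ATP cohort, and a single cohort gives these results a common denominator.
- Section 7.1.2 tabulates ATP exclusions and reasons by site.
- Site is a fixed effect in the model, which absorbs removal that differs only by site.

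These points lower the weight of the finding but do not answer it. Amendment 1 gives a serological reason, not one of compliance, and the June 2019 SAP did not read ATP as requiring serology. The remaining outputs can carry these subjects, because Section 6.10 allows an unknown status and Section 7.3.2 has a missing level for primary diagnosis. The exclusion table shows neither cases nor person-time. Amendment 1 summarises demographics on the ATP cohort only, so removed and retained subjects cannot be compared by age. No analysis of the primary rate without code 2020 is planned.

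A reader might infer three stronger things that the documents do not support:

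- *The exclusion was chosen for its effect on the rate.* The amendment was written with case counts in view (it cites 10 PCR-confirmed cases), but nothing connects this exclusion to its effect on the estimate.
- *The plan holds two rival cohort definitions.* Three places agree on removal, so the intent is clear and Section 5.2.2 looks like a drafting remnant.
- *Dengue cases have been lost or the rate is biased.* No passage says that any removed subject had an episode or how much follow-up was removed.

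**Conclusion.** The point holds as a mismatch between the exclusion and the endpoint, together with an inconsistency in the listed codes. The all-type laboratory-confirmed rate does not use Visit 1 IgG, and the reason for removal does not extend to it.

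The size of the effect cannot be fixed from the documents. The loss of precision is small: about 1% to 5% on the interval width under the assumed 2% to 10%. Bias is zero if incidence is equal. The largest figure shown, −16.7%, needs both 10% removed and a threefold incidence in those removed. A materially distorted primary result is therefore not established. The change is still worth making, because the selection is unnecessary for this endpoint and almost free to avoid.

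**What to change.** 1. Estimate laboratory-confirmed, and confirmed-or-probable, symptomatic incidence that is not split by serostatus on subjects without codes 900 and 2010, which is the June 2019 ATP rule. At minimum, report it with and without code 2020.
2. Apply code 2020 only to inapparent infection and primary/secondary classification. Define the model's event count, and apply code 2020 to any inapparent events in it.
3. List code 2020 with that scope in both Section 5.1 and Section 5.2.2, consistent with Sections 1 and 7.2.2.1.
4. Report the subjects, person-time and cases removed, by site and age.

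The cost is SAP wording, one cohort flag and one extra table, with no new data. The downside is that denominators will differ slightly between endpoints, which a footnote can explain.
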